3.0 Data management

A screening log will be kept electronically on a spreadsheet that is password protected on a secure computer. This log will have the name and demographics of potential participants approached for the study. Separate study numbers for PICS and the interventional trial(s) will be assigned and in case of non-enrolment to either, reasons will be recorded.

Data will be collected directly into paper case report forms that will bear the study number of the participants but no other identifiable information. No data sources (e.g. lab results, etc.) will be stored within the trial files to maintain confidentiality of patients' medical data.

4.0 Statistics

Continuous variables will be compared between the study arms using t-test or Mann Whitney test according to the normality of the study data. Categorical variables (including primary outcome measure) will be compared using the Chi squared test or Fisher exact test as appropriate.

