1.0 Background

Pleural infection is a condition that requires hospitalization for management and is associated with significant in-hospital morbidity and mortality^[1]. Predictors of poor outcome include advancing age, poor nutrition, hospital-acquired infection and impaired renal function.^[2] Medical management is centred on appropriate antibiotic treatment and fluid drainage usually by the means of an intercostal tube. Up to 30% of patients fail medical treatment and referred for surgery.^[3] A recent systematic review of adults patient with pleural infection has shown that the demographics of patients with pleural infection are different in patients from high-income vs lower income countries; the latter being of younger age and lower comorbidity burden.^[4] However, the results of the review did not show significant differences in patient outcomes. The same systematic review pointed to the need for more data from patients residing in lower income countries given that the majority of data is contributed by studies from higher income countries.^[4]

This study aims to prospectively investigate the incidence of pleural infection in a large tertiary centre gathering demographic and clinical data about patients recruited. In addition, the study will examine the different treatment offered and how this related to in-hospital outcomes (length of hospital stay, rate of referral to surgery and mortality).

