2.2.1 Rationale and design

The antiseptic povidone-iodine can safely be instilled into the pleural for the purpose of pleurodesis^[6]. Pleural irrigation with antiseptics is used in adults with open drainage for chronic empyema^[7] and has been described in the acute management of paediatric pleural infection^[8].

This sub-study will investigate the safety and usefulness of povidone-iodine pleural irrigation in 15 eligible patients recruited to PICS. A matched control group will be used and will be composed of 15 patients previously recruited to PICS without receiving povidone-iodine pleural irrigation.

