2.2.4 Outcomes

- Safety: incidence of adverse events (new chest pain, fever, dyspnoea or desaturation) within 24 hours from the first irrigation

- Efficacy

- Time to defervescence
- Time to chest tube removal
- Length of hospital stay
- Need for additional aspiration/tubes

_ Failure of medical treatment

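### The sub-study matches its controls, but the tests named for its continuous outcomes do not use the matching variables; adjusting for one or two of them would be a cheap, optional gain in precision and protection against imbalance.

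*Protocol*

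**What the plan says.** Section 2.2.1 sets the size of the treated group ("This sub-study will investigate the safety and usefulness of povidone-iodine pleural irrigation in 15 eligible patients recruited to PICS") and describes the comparison group: "A matched control group will be used and will be composed of 15 patients previously recruited to PICS without receiving povidone-iodine pleural irrigation". The controls are therefore earlier cohort patients, not randomised ones. The section does not name the matching variables or say whether matching is one-to-one or at group level.

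Section 4.0 is the only statistical text. For continuous outcomes it says: "Continuous variables will be compared between the study arms using t-test or Mann Whitney test according to the normality of the study data". For the rest it says: "Categorical variables (including primary outcome measure) will be compared using the Chi squared test or Fisher exact test as appropriate".

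The efficacy outcomes in section 2.2.4 include three continuous ones: the time until fever resolves, "Time to chest tube removal" and "Length of hospital stay". Section 1.0 gives a reason to expect baseline variables to matter: "Predictors of poor outcome include advancing age, poor nutrition, hospital-acquired infection and impaired renal function". Section 2.1.5 has the RAPID score collected for the cohort.

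**The concern.** Matching on a variable that predicts outcome makes the outcomes of matched patients alike. A Mann-Whitney test treats the groups as independent. The t-test is not stated to be paired, and as the alternative to Mann-Whitney it reads most naturally as unpaired. Neither takes up the matching variables.

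Two things can follow, and they point in opposite directions:

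- If matching has balanced the groups, the unadjusted test overstates the standard error and is conservative.
- If imbalance remains, as is possible with non-randomised earlier controls, the unadjusted difference carries that imbalance as bias, and the test can be anti-conservative.

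At stake are three efficacy outcomes with 15 patients per group. The primary outcome is not affected, because section 4.0 treats it as categorical.

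**Working it through.** **Inputs.** The protocol supplies only 15 v 15. It gives no significance level, power, effect size, SD or strength of prediction, so it has no figure of its own to reproduce. Assumed here: two-sided 5%, total outcome SD 1 and a true effect of 0.8 SD. R² is the share of outcome variance explained by the matching variable, varied from 0 to 0.5. r is the correlation of that variable between matched patients (1 = exact matching).

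**Step 1: standard error.** The unadjusted test estimates the variance of the difference as 2·SD²/15. With balanced matching it is 2·SD²·(1 − r·R²)/15. The excess in standard error is 1/√(1 − r·R²) − 1.

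- R² 0.1, r 1: 1/√0.90 − 1 = 5%
- R² 0.3, r 1: 1/√0.70 − 1 = 20%
- R² 0.5, r 1: 1/√0.50 − 1 = 41%
- R² 0.3, r 0.7: 1/√0.79 − 1 = 13%
- R² 0.3, r 0.5: 1/√0.85 − 1 = 8%

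**Step 2: type I error and power, groups balanced.** Simulated data sets of 15 v 15 with exact matching; the regression is on group plus the matching variable.

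| R² | Type I error, t-test | Type I error, regression | Power, t-test | Power, regression |
|---|---|---|---|---|
| 0 | 5% | 5% | 56% | 56% |
| 0.1 | 4.0% | 5% | 57% | 61% |
| 0.3 | 2.2% | 5% | 57% | 71% |
| 0.5 | 0.8% | 5% | 59% | 85% |

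Mann-Whitney power is 52% to 54% over the same range.

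**Step 3: how much of the power gain is due to matching?** At R² 0.3, t-test v regression gives 57% v 71% (r 1), 57% v 71% (r 0.7), 57% v 70% (r 0.5) and 56% v 70% (r 0, no matching). The gain is nearly constant, so it comes from adjusting for a prognostic variable. What matching itself produces is the conservative type I error.

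**Step 4: imbalance left after matching.** Suppose the groups still differ by 0.5 SD on the variable and R² is 0.3. The unadjusted difference is then biased by 0.5 × √0.3 = 0.27 SD. With r between 0.5 and 0.7, the type I error of the nominal 5% t-test is about 9%.

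**Step 5: what adjustment can cost.**

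- One uninformative variable: under 1 point of power with complete data (56.4% v 56.3%) and with 20% of values missing at random (45.9% v 45.3%).
- Four uninformative variables: about 5 points (56% to 51%).
- Four covariates of which one is informative at R² 0.1: 55% with regression v 57% unadjusted, a small net loss.
- Skewed times left untransformed, with an uninformative variable: regression on raw lognormal values has 46% power, against 52% for Mann-Whitney and 56% for regression on the log scale.

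**The case against.** The strongest case against is that the planned tests are usable, that section 4.0 is two generic sentences, that it does not say the t-test is unpaired, and that covariate adjustment is commonly left to an analysis plan, which may exist but is not at hand. Almost every figure above is assumed, and the protocol makes no power claim that could be wrong. Much of this stands, and it limits the point to an optional improvement. It does not remove it: section 4.0 names specific tests, and as worded they do not take up the matching that section 2.2.1 builds in.

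It also stands that the power gain is not caused by ignoring the matching; step 3 shows this.

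A further objection concerns outcomes that may never be observed. Section 1.0 reports: "Up to 30% of patients fail medical treatment and referred for surgery". Death or surgery can leave the fever or tube-removal time undefined. A regression on log time cannot hold such values, and treating them as missing at random would be wrong, since failure is related to outcome. A rank test can place them last. This stands, and the fix has to keep a rank analysis for them.

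A reader might infer that, because ignoring matching is conservative, the plan carries no false-positive risk. The documents do not support this: the controls are non-randomised, nothing guarantees balance, and step 4 shows the error rate rising under imbalance. A reader might equally infer that the main analysis is invalid. That is not supported either: the primary outcome is categorical, and the planned tests for the continuous outcomes remain usable.

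**Conclusion.** The mismatch between the matched design and the tests worded for continuous outcomes is real, but modest in consequence. This is an optional improvement in efficiency and protection against bias; it does not show an invalid primary analysis.

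The direction of the error depends on balance: conservative if the groups are balanced on prognostic matching variables, possibly anti-conservative if they are not. Its size cannot be fixed from the protocol, which gives neither the matching variables nor their strength for these outcomes. If they explain 10% of variance or less, the standard error excess is about 5% or less and power gains about 4 points at most (57% to 61%). If they explain 30%, the gain is about 14 points (57% to 71%). These figures rest on the assumed 5% two-sided level, the 0.8 SD effect and a linear relation on the analysis scale.

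**What to change.** - **Section 2.2.1:** name one or two matching variables, for example the RAPID score, which is already collected, and say whether matching is one-to-one or at group level.
- **Section 4.0:** make linear regression on group plus those variables the main analysis of the continuous sub-study outcomes, with skewed times log-transformed. Keep the t-test or Mann-Whitney test as a supporting analysis, and use a rank analysis for times left undefined by death or surgery.
- **Unchanged:** the chi-squared and Fisher tests for the categorical outcomes.

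A paired test is the weaker choice as main method. It needs one-to-one pairs and loses the whole pair when either value is missing. With 15 pairs it gives a wider interval than the unpaired test unless the within-pair correlation exceeds about 0.09.

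The change needs wording in both sections and no new data if the variables are ones already collected. The statistical price is about 1 to 2 points of power at most if a single variable proves uninformative, but about 5 points with four, so the number must be kept small. Adjustment removes bias only from the variables that are included.

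### Section 4.0 names only chi-squared or Fisher tests for categorical outcomes; at 15 v 15 these say little about safety or failure, and the safety outcome has no defined control count

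*Protocol*

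**What the plan says.** Protocol Section 2.2.1 sets the aim and the size: "This sub-study will investigate the safety and usefulness of povidone-iodine pleural irrigation in 15 eligible patients recruited to PICS". The comparison group is described next: "A matched control group will be used and will be composed of 15 patients previously recruited to PICS without receiving povidone-iodine pleural irrigation". No derivation, power or target effect accompanies these numbers.

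Section 2.2.4 defines the safety outcome as follows: "Safety: incidence of adverse events (new chest pain, fever, dyspnoea or desaturation) within 24 hours from the first irrigation". Under efficacy it lists three durations and two yes/no outcomes, namely further aspiration or tubes and "Failure of medical treatment". None is labelled primary.

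Section 4.0 then covers every categorical outcome in one sentence: "Categorical variables (including primary outcome measure) will be compared using the Chi squared test or Fisher exact test as appropriate". It gives no significance level, no sidedness, no estimate with an interval, and no guidance on how to read a non-significant result.

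The only failure rate in the protocol is in Section 1.0: "Up to 30% of patients fail medical treatment and referred for surgery".

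**The concern.** The sub-study asks whether irrigation is safe and useful. For its yes/no outcomes, the one analysis fixed in the protocol is a test of difference between two groups of 15.

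For safety, such a test is a weak instrument. With so few patients it will usually fail to reject even when irrigated patients have clearly more events, and a reader could take that as reassurance. For failure of medical treatment, a large true benefit could easily come out non-significant and be taken as no effect.

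There is also a problem of definition. The safety window opens at the first irrigation. Controls are not irrigated, so the protocol does not say over which 24 hours their events would be counted.

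What 15 patients can supply is an estimated event rate with an honest statement of its uncertainty. Section 4.0 does not ask for one.

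**Working it through.** **Inputs.** Group sizes 15 and 15 (Section 2.2.1). Tests: chi-squared or Fisher (Section 4.0). Control failure rate: 30% as a ceiling (Section 1.0). Alpha and sidedness are not in the protocol; two-sided 0.05 is assumed and alternatives are shown. The protocol states no power or sample-size derivation, so it has no figure to reproduce.

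**1. Which test applies.** With equal groups, the smallest expected count is half the total number of events when events are the rarer category. With 4 events in all it is 4 × 15/30 = 2.0. Under the usual rule (expected count below 5) this selects Fisher's test.

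**2. What the test calls significant.** For *a* events against none, the two-sided Fisher p-value is 2 × C(15,*a*)/C(30,*a*).

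- 4 v 0: 2 × 1365/27405 = 0.0996. One-sided: 1365/27405 = 0.0498.
- 5 v 0: 2 × 3003/142506 = 0.042, the first two-sided result below 0.05.
- With one event in the other arm: 6 v 1 gives 0.080 and 7 v 1 gives 0.035.

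Uncorrected chi-squared for 4 v 0 is 30 × (4 × 15 − 0 × 11)²/(15 × 15 × 4 × 26) = 108000/23400 = 4.62, p = 0.032. With Yates' correction it is 30 × (60 − 15)²/23400 = 2.60, p = 0.107.

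**3. Power.** If one arm has a true rate of zero, Fisher rejects only when the other arm has at least 5 events, and uncorrected chi-squared when it has at least 4. At a rate of 30%, P(X ≥ 5) for X ~ Binomial(15, 0.3) is 0.485 and P(X ≥ 4) is 0.703. The other rows come from exact enumeration of both binomials.

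| True rates | Fisher, two-sided 0.05 | Uncorrected chi-squared |
|---|---|---|
| 30% v 0% | 48.5% | 70.3% |
| 30% v 10% | 14.9% | 27.8% |
| 20% v 0% | 16.4% | 35.2% |
| 10% v 0% | 1.3% | 5.6% |

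The last two rows can be read as harm (adverse events in irrigated patients against none) or as complete prevention of failure from a lower control rate.

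**4. What estimation would show.** Exact (Clopper-Pearson) 95% intervals for the irrigated group:

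- 0/15: upper limit 1 − 0.025^(1/15) = 21.8%.
- 1/15: 0.2% to 31.9%.
- 4/15 = 26.7%: 7.8% to 55.1%.

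For failure in 4/15 controls against 0/15 irrigated, the difference is 26.7 points, with Newcombe 95% interval 0.9 to 52.0.

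**5. The control count for safety.** Section 2.2.4 starts the clock at the first irrigation. Section 2.2.1 draws controls from patients who had none. Neither section gives controls a substitute starting point, so the second row of a 2 × 2 safety table is undefined. The 4 v 0 table above therefore shows how the test behaves, not a count the protocol says how to obtain.

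**The case against.** A reader might infer that the protocol will judge safety by significance, so that a harmful or a fully effective irrigation would be reported as no different from control. The document does not support that. Section 4.0 says that variables will be compared. It sets no threshold and no rule that a non-significant result means safe or ineffective. What can be said is that nothing in the section guards against that reading.

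Other parts of the case against carry weight:

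- **The figures depend on assumptions.** Uncorrected chi-squared or one-sided Fisher would call 4 v 0 significant, and chi-squared raises the power for 30% v 0% to about 70%. The clause "Chi squared test or Fisher exact test as appropriate" leaves room for either test, though convention at these counts points to Fisher. This stands as a caveat. It also shows that a borderline result would turn on the choice of test; the Newcombe interval above likewise excludes zero where two-sided Fisher gives 0.10.
- **30% is an upper figure** for pleural infection in general, and the sub-study takes a selected group. This affects the size but not the direction, since a lower control rate gives less power.
- **Three of the five efficacy outcomes are durations**, compared by t-test or Mann-Whitney. Low power on failure does not show that a benefit would be missed altogether.
- **Section 2.2.4 already words safety as an incidence**, which fits a one-group estimate. This is fair. The step missing is to carry that into Section 4.0 with an interval.
- **The listed adverse events are not graded**, so these figures concern events of any severity, not serious harm.
- **A separate analysis plan may add intervals.** It may, and their absence alone would be no finding. The point is that the analysis the protocol does fix is poorly suited to the safety aim and undefined for controls.

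Matching does not rescue the comparison: an exact McNemar test with 4 discordant pairs against 0 gives 2 × 0.5⁴ = 0.125.

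**Conclusion.** The point holds as a limited, cheaply remedied weakness in Section 4.0. Assuming two-sided alpha 0.05 and Fisher's test, 4 events against none gives p = 0.10. Complete elimination of a 30% failure rate would be non-significant about 52% of the time (about 30% with uncorrected chi-squared). A fall from 30% to 10% would be detected about 15% of the time (28%). The lack of a defined control count for safety follows from Sections 2.2.1 and 2.2.4 and needs no assumption.

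It does not follow that the protocol equates non-significance with safety or with no effect, or that its conclusions will be wrong. The defect is that its one stated analysis of these outcomes is uninformative at this size and leaves a non-significant result open to that reading.

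**What to change.** In Section 4.0:

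- Make the main safety analysis the proportion of irrigated patients with an adverse event, with an exact (Clopper-Pearson) 95% confidence interval.
- Report arm differences in failure of medical treatment and in further drainage with 95% confidence intervals alongside any test, and name the interval method in advance.
- State that a non-significant p-value will not be taken as evidence of safety or of no effect.

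In Section 2.2.1, note that 0 events in 15 patients excludes only true rates above about 22%.

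The cost is a few sentences in two sections, with no extra patients, data or procedures. The downside is that the claim the sub-study can make is stated less favourably.
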